On Day -3 (Admission), after all inclusion/exclusion criteria are checked, all eligible subjects will be enrolled and then perform a product test using up to 5 CHTPs 1.2. However, before smoking and the product testing, the sample for CYP2A6 activity has to be taken. After the product test, subjects not willing and ready to use the CHTP 1.2 will be discontinued. All subjects that are not enrolled are considered as screen failures. After the sample for CYP2A6 activity has been taken, and the product test has been performed, smokers will be allowed to smoke their single preferred brand of CC *ad libitum* until 11:00 PM. Use of any tobacco/nicotine containing product other than CC and CHTP 1.2 for the product test will not be allowed after Admission.

- The Baseline Period (from Day -2, 06:30 AM until Day 1, 06:29 AM):

All subjects will continue smoking their CC *ad libitum*. Twenty four-hour urine collection for Day -2 will start in the morning of Day -2 ending in the morning of Day -1. Twenty four-hour urine collection for Day -1 will start in the morning of Day -1 ending in the morning of the Day 1. On Day -2 and Day -1, smoking will be allowed from 06:30 AM until around 11:00 PM. However, on Day -2, smoking will be allowed only after the Cough Questionnaire has been completed.

On Day -1, subjects will be randomized to 1 of the 2 study arms in a 2:1 ratio using a stratified randomization.

- CHTP 1.2 arm: ~80 subjects, *ad libitum* use of CHTP 1.2.
- CC arm: ~40 subjects, *ad libitum* use of their own preferred CC brand.

Subjects will be informed about their randomized study arm by the study site staff on Day 1 prior to 06:30 AM. Subjects who do not complete the study after randomization will not be replaced.

Confidentiality Statement

Data and information contained in this document are considered to constitute trade secrets and confidential commercial information, and the legal protections provided to such trade secrets and confidential information are hereby claimed under the provisions of applicable law. No part of this document may be publicly disclosed without the written consent of Philip Morris Products S.A.

- The Exposure Period (from Day 1, 06:30 AM until Discharge at Visit 4):

The exposure period will include both the exposure period in confinement, and the exposure period in the ambulatory setting:

- The Exposure Period in the Confinement Setting (from Day 1, 06:30 AM until the time of Discharge on Day 6):

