The exposure period in confinement consists of 5 days of *ad libitum* use of the assigned product (CHTP 1.2 or CC, exclusively) from 06:30 AM until around 11:00 PM each day. Subjects who are willing to attempt quitting using any tobacco products during the study will be encouraged to do so and will be referred to a smoking cessation aid service.

Use of any tobacco/nicotine containing product other than the assigned product will not be allowed and may, at the discretion of the Investigator, result in the subject's discontinuation from the study.

24-hour urine will be collected from Day 1 to Day 5 on site ending in the morning of Day 6. On Day 1, product use must not start prior to the end of urine collection of Day -1. The end of the 24-hour urine collection period for Day 5 will end in the morning of Day 6 prior to Discharge.

Procedures on Day 6 will be conducted before discharge of the subject from the clinic after 9 days in a confined setting. Use of products will be allowed on Day 6 according to product allocation, but only after the sample for CYP2A6 activity has been taken, the cough assessment has been completed, and spirometry has been performed.

Subjects will be instructed to continue their assigned product/regimen in an ambulatory setting for 85 days.

- The Exposure Period in the Ambulatory Setting (from Discharge on Day 6 until Discharge at Visit 4):

At the end of the confinement period prior to Discharge on Day 6, subjects will be instructed to continue their assigned product/regimen in an ambulatory setting for 85 days.

Subjects will be required to make three visits (Visit 2, Visit 3 and Visit 4) to the investigational site. Each visit will cover 2 consecutive days on site. For Visit 2 and Visit 3, the subject will check-in in the morning on the first day of the respective visit and will check-out on the second day of the visit. For Visit 4, the subject will check-in in the morning on the first day of the visit, and will be discharged on the second day of the visit after having performed all the safety examination procedures.

Confidentiality Statement

Data and information contained in this document are considered to constitute trade secrets and confidential commercial information, and the legal protections provided to such trade secrets and confidential information are hereby claimed under the provisions of applicable law. No part of this document may be publicly disclosed without the written consent of Philip Morris Products S.A.

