6.4 Method for Assigning Subjects to Study Arms

At the end of the Baseline period enrolled subjects will be randomized using an interactive web and voice response system (IxRS) on Day -1 at any time during the day. Subjects will be informed of their randomized study arm in the morning of Day 1, prior to 06:30 AM (the start of the exposure period). Subjects will be randomized to one of the 2 study arms: CHTP 1.2 or CC in a 2:1 ratio.

Stratified randomization will be conducted by sex and by average daily CC consumption over the last 6 weeks prior to Admission as self-reported (smoking 10 to 19 CC/day vs. > 19 CC/day). In each arm, each sex and each of the smoking strata will have a quota applied to ensure they represent at least 40% of the population.

Confidentiality Statement

Data and information contained in this document are considered to constitute trade secrets and confidential commercial information, and the legal protections provided to such trade secrets and confidential information are hereby claimed under the provisions of applicable law. No part of this document may be publicly disclosed without the written consent of Philip Morris Products S.A.

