9.2.3 Exposure Period (Days 1 to 5)

[Table 9](#) shows the assessments that will be performed on Day 1.

The collection of 24-hour urine of Day 1 starting on Day 1 will end on Day 2.

Table 9 Time Schedule – Day 1

Time	Blood Sample	Procedures	Additional Information
		Day 1	
		Allocation to study arm	
6:30 AM		Start of use of IPs	
Prior to 11:30 AM		AE/SAE recording	
Prior to 11:30 AM		Concomitant medications	
Prior to 11:30 AM		End of 24-hour urine sample collection for Day -1	The urine is collected for 24 hours \pm 1 hour. The end of the 24-hour urine collection should be prior to first use of IPs.
Prior to 11:30 AM		Start of 24-hour urine sample collection for Day 1.	The start of 24-hour urine collection of Day 1 should be subsequent to the end of 24-hour urine collection of Day -1
Prior to 11:30 AM		Urine sample to be taken from the 24-hour urine of Day -1	Aliquots from 24-hour urine will be collected according to Table A2 . Bio-banking for biomarkers (if additional consent is obtained)
Prior to 11:30 AM		Vital signs (blood pressure, pulse rate, respiratory rate)	At least 5 minutes in supine position, at least 15 minutes after having stopped using IP
Prior to 11:30 AM		Assessment of cough (VAS)	Has to be done prior to allocated IPs

Confidentiality Statement

Data and information contained in this document are considered to constitute trade secrets and confidential commercial information, and the legal protections provided to such trade secrets and confidential information are hereby claimed under the provisions of applicable law. No part of this document may be publicly disclosed without the written consent of Philip Morris Products S.A.

Time	Blood Sample	Procedures	Additional Information
Start of Procedure		Day 1	
In the evening prior to 9:30 PM (approx. 8:00 PM ± 1.5 hour)		CO breath test	
In the evening prior to 9:30 PM (approx. 8:00 PM ± 1.5 hour)	√	COHb in blood	
In the evening prior to 9:30 PM (approx. 8:00 PM ± 1.5 hour)	√	Plasma nicotine and cotinine sample	Cotinine will be measured in the same assay as nicotine. No additional blood samples required
8:00 PM - 11:00 PM		QSU brief Questionnaire	
8:00 PM - 11:00 PM		MCEQ Questionnaire	
11:00 PM		End of use of IPs	
6:30 AM - 11:15 PM		Collection of used CC butts	For accountability
6:30 AM - 11:15 PM		Collection of used CHTP 1.2	For accountability

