12.1.2 Definitions for Statistical Data Analysis

Baseline:

Unless specified, Baseline is defined as the last available time point prior to first product use in the Exposure Period.

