U: Bio-banking for BoExp and clinical risk endpoints ⁿ					•					•						•	
B: Bio-banking for transcriptomics, lipidomics and DNA methylation sequencing ^{n, o}				•						•						•	

Abbreviations: 4-HNE = 4-Hydroxy-2-nonenal; 8-epi-PGF2 α = 8-epi-prostaglandine F2 α ; 8-OHdG = 8-Hydroxy-2'-deoxyguanosine; 11-DTX-B2 = 11-dehydro-thromboxane B2; AE = Adverse event; Apo = Apolipoprotein; B = Blood sample required; BMI = Body mass index; BoExp = Biomarker(s) of exposure; CC = Combustible cigarette(s); CHTP 1.2 = Carbon Heated Tobacco Product 1.2; CO = Carbon monoxide; COHb = Carboxyhemoglobin; CYP1A2 = Cytochrome P450 1A2; CYP2A6 = Cytochrome P450 2A6; DNA = Deoxyribonucleic acid; FTND = Fagerström Test for Nicotine Dependence; HbA1c = Hemoglobin A1c; HDL = High density lipoprotein; HIV = Human immunodeficiency virus; hs-CRP = High-sensitive C-reactive protein; LDL = Low density lipoprotein; MCEQ = Modified Cigarette Evaluation Questionnaire; MPO = Myeloperoxidase; PGF2 α = prostaglandine F2 α ; QSU-brief = Questionnaire of Smoking Urges (brief version); SA = Smoking abstinence; SAE = Serious adverse event; sICAM-1 = Soluble inter-cellular adhesion molecule; TAC = Total anti-oxidant capacity; U = Urine sample required; WBC = White blood cell count; TC = Total cholesterol, TG = Triglycerides.

- ^a Systolic and diastolic blood pressure, pulse rate, and respiratory rate (systolic and diastolic blood pressure will also be analyzed as risk markers on Day -1, Day 6, Visit 2, Visit 3, and Visit 4 (first day of the respective visits).
- ^b Including height (only at the Screening Visit).
- ^c Spirometry without bronchodilator will be performed at the Screening Visit (Visit 1) at least 1 hour after having stopped smoking and must be done prior to spirometry with bronchodilator.
Spirometry post-bronchodilator will be done at Visit 1, on Day 6 and at Visit 4. On Day 6 and Visit 4, spirometry post-bronchodilator will be performed prior to product use (CC or CHTP 1.2).
- ^d Pre-study chest X-ray (with anterior-posterior and left lateral views) may be used if performed within 6 months prior to Screening.

Confidentiality Statement

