12.1.4 Definitions for Statistical Data Analysis

The following definitions (**Table 17**) for statistical analyses/presentations will be used:

Table 17: Definition of terms for the statistical analysis

Term	Definition
Baseline Value	The last valid assessment at the last available time point prior to first product use in the Exposure Period.

For 24-hour urine collections, the collection sample will be labelled by the day in which the collection started. As an example if the 24-hour urine sample is collected from Day 5 to Day 6, it will be analyzed and reported as the Day 5 sample.

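### The first-use baseline rule lets baseline blood pressure, pulse and respiratory rate come from Day 1 in some subjects and Day -1 in others, decided after the arm is known; the SAP should name Day -1 for these measures

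*Protocol*

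**What the plan says.** **Baseline.** Protocol 12.1.2 gives "Unless specified, Baseline is defined as the last available time point prior to first product use in the Exposure Period". SAP 12.1.4, Table 17, gives "The last valid assessment at the last available time point prior to first product use in the Exposure Period" and lists no exception.

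**Arm known before use.** Protocol 4.1 states: "Subjects will be informed about their randomized study arm by the study site staff on Day 1 prior to 06:30 AM". SAP 6.3.1 says the same.

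**Use is at the subject's choice.** Protocol 4.1: "The exposure period in confinement consists of 5 days of *ad libitum* use of the assigned product (CHTP 1.2 or CC, exclusively) from 06:30 AM".

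**Day 1 vital signs.** Protocol Table 9 schedules them before 11:30 AM, with the note "At least 5 minutes in supine position, at least 15 minutes after having stopped using IP". The Day 1 cough row of the same table carries a different instruction: "Has to be done prior to allocated IPs".

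**Blood pressure as a risk marker.** Footnote a of Protocol Table A1 says "systolic and diastolic blood pressure will also be analyzed as risk markers on Day -1, Day 6, Visit 2, Visit 3, and Visit 4". The SAP appendix of study assessments repeats this footnote. SAP 12.5.2.6, however, lists blood pressure at baseline without a day, although HbA1c in the same list is given as Day -1.

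**Safety tables.** SAP 12.5.4.5.2 summarises blood pressure, pulse and respiratory rate as change from baseline on each later confinement day and at the ambulatory visits. It names no baseline day.

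**The concern.** A baseline should be fixed before allocation can influence it. Here the cut-off is the subject's own first use on Day 1, after the arm has been disclosed. Whether the Day 1 reading counts as baseline depends on which came first, the measurement or the first product. That order depends on site scheduling and on how soon the subject chooses to use the assigned product.

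Two things are at stake. Baseline blood pressure is the covariate in the ANCOVA of SAP 12.5.2.6, and baseline is the reference for all vital-sign change tables. In addition, Day 1 would be the baseline row for some subjects and a post-baseline row for others in the same table. If subjects given an unfamiliar product tend to start later than subjects given their usual cigarettes, the mixture would differ by arm.

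**Working it through.** **Step 1. Do the windows overlap?** Product use on Day 1 opens at 06:30 AM and the vital-signs window closes at 11:30 AM, an overlap of 11.5 − 6.5 = 5.0 hours. A reading before first use and a reading after it (with the 15-minute wait) both comply with Table 9. Only the cough row requires measurement before use.

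**Step 2. Which day does each order give?**

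| Order on Day 1 | Baseline under SAP Table 17 | Risk-marker day in Table A1 footnote a |
|---|---|---|
| Reading, then first use | Day 1 | Day -1 (blood pressure only) |
| First use, then reading | Day -1 | Day -1 (blood pressure only) |

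The first row is the conflict for blood pressure. For pulse and respiratory rate the last column is empty, so there is ambiguity but no contradiction.

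**Step 3. Are the two readings taken under the same conditions?** Smoking stops at about 11:00 PM. A pre-use Day 1 reading at 06:30 AM or later therefore follows about 7.5 hours or more without product. Day -1 vital signs (Protocol Table 8) are also due before 11:30 AM with smoking open from 06:30 AM, so they may fall before or after smoking. Day -1 is itself uncontrolled for smoking state, but its readings precede disclosure of the arm.

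**Step 4. Which other endpoints are touched?** Protocol 7.6.2.1 requires the Day -1 urine collection to end before Day 1 product use, so the urinary baseline is normally the Day -1 sample. COHb is drawn at about 8:00 PM, so its last pre-use value is Day -1 unless a subject uses nothing until after the Day 1 evening draw.

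**Step 5. How large could the effect be?** The documents give no inputs, so all of these are assumptions:
- a pre-use Day 1 systolic reading is lower than the Day -1 reading by d = 3, 5 or 8 mmHg;
- between-subject SD is 8 and within-subject SD is 6 (variances 64 and 36);
- 80 and 40 subjects are analysed, the planned randomised numbers;
- pT and pC are the shares with a Day 1 baseline in the CHTP 1.2 and CC arms;
- there is no true product effect.

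Formulas:
- shift in mean change within an arm = p × d;
- bias in the difference in mean change = (pT − pC) × d;
- ANCOVA bias = slope × (pT − pC) × d, with slope = 64 / (100 + v);
- v = d² × [80 pT(1 − pT) + 40 pC(1 − pC)] / 120, the extra baseline variance from the mixture.

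With pT = 0.60 and pC = 0.20, v = d² × (19.2 + 6.4)/120 = 0.2133 d².

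| d (mmHg) | v | slope | bias in difference of mean changes (0.40 d) | ANCOVA bias |
|---|---|---|---|---|
| 3 | 1.92 | 0.628 | 1.2 | 0.75 |
| 5 | 5.33 | 0.608 | 2.0 | 1.2 |
| 8 | 13.65 | 0.563 | 3.2 | 1.8 |

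The standard error of the adjusted difference is √[(100 − 64 × slope) × (1/80 + 1/40)], about 1.5 mmHg. Simulation under the same assumptions gave ANCOVA biases of 0.75, 1.17 and 1.83.

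With pT = pC = 0.50, both biases in the arm contrast are zero, while mean change within each arm still moves by 0.5 d = 1.5 to 4 mmHg.

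**The case against.** The last value before first exposure is a conventional baseline. The qualifier opening Protocol 12.1.2 allows exceptions, and footnote a, which lists Day -1 and omits Day 1, can fairly be read as one. The 15-minute wait in Table 9 suggests that Day 1 vital signs were meant as exposure readings, and nothing shows that pre-use readings would be common.

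Much of this stands for the Protocol. It does not settle the SAP: Table 17 has no such qualifier, 12.5.2.6 says only baseline for blood pressure, and the repeated footnote sits in an assessment schedule, not in the analysis definitions. For pulse and respiratory rate no exception exists in either document.

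A reader might also infer more than the documents support:
- **That pulse and respiratory rate contradict a named Day -1.** Footnote a names only systolic and diastolic pressure as risk markers.
- **That an abstinent Day 1 baseline is being mixed with a smoking-state Day -1 baseline.** Day -1 readings may also precede smoking (Step 3). Naming Day -1 therefore removes the dependence on allocation but does not standardise smoking state.
- **That baseline COHb is compromised.** This would need a confined smoker of at least 10 cigarettes a day to use nothing until after an evening draw, which is remote.
- **That baseline should be re-anchored to a fixed clock time for all endpoints.** The Day -1 urine collection and the pre-use Day 1 cough assessment can both end after 06:30 AM and could be disqualified. Restricting baseline to the Baseline Period would remove the Screening spirometry and Day -3 CYP2A6 values.

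**Conclusion.** The point holds for vital signs. As the SAP is written, baseline blood pressure, pulse and respiratory rate can come from Day 1 or Day -1 according to events after allocation. For blood pressure as a risk marker this disagrees with the schedule footnote.

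The reach is limited to the secondary blood-pressure analysis, which has no multiplicity adjustment, and to descriptive safety tables. Sample size, power and the confirmatory claim are unchanged.

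It would be tempting to conclude that the arm contrast is biased. The documents do not show that: bias requires the share with a Day 1 baseline to differ between arms, and no text gives those shares or the Day 1 to Day -1 difference. The 0.75 to 1.8 mmHg range rests wholly on the assumptions in Step 5 and is zero when the shares are equal. The case for change is that the ambiguity and the post-allocation dependence can be removed with data already scheduled for collection.

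**What to change.** Keep the general first-use definition for all other endpoints, including urinary biomarkers, COHb, cough, spirometry and CYP2A6. Add one entry to SAP Table 17, with matching wording in SAP 12.5.2.6 and 12.5.4.5.2:

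- baseline for systolic and diastolic blood pressure, pulse rate and respiratory rate is the Day -1 reading for every subject;
- if the Day -1 reading is missing, the Day -2 reading is used;
- Day 1 vital signs are summarised as a post-allocation timepoint and never serve as baseline.

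The Protocol definition can stay, since its qualifier permits a specified exception. The cost is a short SAP revision and one derivation rule. No new measurements are needed, because vital signs are already scheduled on Day -2 and Day -1.

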12.1.3 Descriptive Statistics

All data will be presented in listings, ordered by product arm and subject, unless otherwise specified.

Descriptive statistics (number of subjects [n], number and percent of subjects with missing data, the arithmetic mean, arithmetic standard deviation (SD), median, first and third quartiles, minimum and maximum for continuous data, including geometric mean and coefficient of variation (CV) for data analyzed in the log scale; frequency counts and percentages for categorical data) will be presented overall and at each time point, where applicable.

For BoExp, the geometric mean and CV will be presented in addition to the mean and SD.

Confidentiality Statement

Data and information contained in this document are considered to constitute trade secrets and confidential commercial information, and the legal protections provided to such trade secrets and confidential information are hereby claimed under the provisions of applicable law. No part of this document may be publicly disclosed without the written consent of Philip Morris Products S.A.

12.1.4 Handling of Missing Values and of Values outside the Detection Limits

Descriptive summaries will be provided for the evaluable data with no imputation.

Missing values for the endpoints analyzed via the mixed model method will not be directly imputed as they are handled within the analysis itself.

Values below the lower limit of quantification (LLOQ) will be imputed using $0.5 \times \text{LLOQ}$. For values above the upper limit of quantification (ULOQ), the ULOQ will be used for calculation and reporting in summary tables. The number of values below LLOQ or above ULOQ will be presented in each summary table. If 50% or more data are below LLOQ or above ULOQ, only the number (%) of value below LLOQ or above ULOQ will be reported in the summaries, together with minimum and maximum of the observed values.

For questionnaire data, total scores and domain or subscale scores may use a certain degree of imputation by averaging across individual item scores.

Further details will be provided in the SAP.

12.1.5 Significance Level for Inferential Analysis

Unless stated otherwise, all statistical tests will be conducted using a one-sided test with 2.5% type I error probability, and all quoted confidence intervals (CIs) will be two-sided 95% CIs.

The primary endpoints will be tested using a multiple testing procedure to preserve the overall alpha level by simultaneously testing the endpoints using a closed procedure with each test performed at the one-sided 2.5% type I error probability. This implies that statistical significance is required for all primary endpoints in order to be able to make confirmatory claims about any of the endpoints.

Full details of this approach will be provided in the SAP.

12.2 Determination of Sample Size and Power Consideration

The following discussion addresses the ability to detect a reduction of 50% or more in the levels of MHBMA, 3-HPMA, S-PMA, and COHb on Day 5 and in total NNAL after 90 days in smokers switching from CC to the CHTP 1.2 as compared to smokers continuing to use CC, using a one-sided test with 2.5% type I error probability.

[Table 20](#) describes the expected coefficients of variation (CV) and mean ratios (MR) between CHTP 1.2 and the one control arm based on data from a controlled, randomized, open-label, 3-arm parallel single-center confinement study that investigated exposure to selected smoke constituents in smokers switching from CC to smoking article cigarettes for 5 days, the YVD-CS01-EU study (ClinicalTrials.gov ID: NCT00812279) sponsored by PMI.

Confidentiality Statement

Data and information contained in this document are considered to constitute trade secrets and confidential commercial information, and the legal protections provided to such trade secrets and confidential information are hereby claimed under the provisions of applicable law. No part of this document may be publicly disclosed without the written consent of Philip Morris Products S.A.

Table 20 Expected Mean Ratios and Coefficients of Variation for CHTP 1.2/CC after 5 Days of exposure

	CHTP 1.2/CC MR (CV)
COHb	0.40 (0.32)
3-HPMA	0.30 (0.50)
MHBMA	0.15 (0.70)
S-PMA	0.20 (0.70)

Abbreviations: 3-HPMA = 3-hydroxypropylmercapturic acid; CC = Combustible cigarettes; COHb = Carboxyhemoglobin; CV = Coefficients of variation; MHBMA = Monohydroxybutenyl mercaptyuric acid; MR = Mean ratios; S-PMA = S-phenylmercapturic acid; CHTP 1.2 = Carbon Heated Tobacco Product 1.2.

Table 21 describes the expected coefficients of variation (CV) and mean ratios (MR) in total NNAL after 90 days between CHTP 1.2 and the one control arm based on a randomized, controlled, forced-switching, open-label, parallel-group, single-center study in 90 male and female adult smokers to evaluate six biomarkers of tobacco smoke exposure over a 12-week period of unrestricted smoking in the participants' normal life setting [48].

Table 21 Expected Mean Ratios and Coefficients of Variation for CHTP 1.2/CC after 90 Days of exposure

	CHTP 1.2/CC MR (CV)
Total NNAL	0.30 (0.60)

Abbreviations: Total NNAL = Total 4-(methylnitrosamino)-1-(3-pyridyl)-1-butanol; MR = Mean ratio; CHTP 1.2 = Carbon Heated Tobacco Product 1.2; CC = Combustible cigarettes; CV = Coefficient of variation.

The power to detect a reduction was computed.

Table 22 describes the expected power to detect a reduction of 50% or more in the levels of MHBMA, 3-HPMA, S-PMA, and COHb in CHTP 1.2 arm compared to the CC arm after 5 days of exposure and total NNAL after 90 days of exposure, with a one sided test with 2.5% type I error probability using the assumptions from YVD-CS01-EU and, and 120 randomized subjects in a 2:1 ratio (80 in CHTP 1.2 arm and 40 in CC arm). It is assumed that a minimal number of subjects will be excluded from the PP set in confinement for both arms and CC in ambulatory, whereas at least 50% will remain in the PP set in ambulatory for CHTP 1.2, therefore a 2:1 randomization ratio was chosen.

Confidentiality Statement

Data and information contained in this document are considered to constitute trade secrets and confidential commercial information, and the legal protections provided to such trade secrets and confidential information are hereby claimed under the provisions of applicable law. No part of this document may be publicly disclosed without the written consent of Philip Morris Products S.A.

Table 22 Expected Power

Assumptions	Reduction					
	50%	51%	52%	53%	54%	55%
YVD-CS01-EU	94%	88%	81%	70%	56%	38%

The test-wise powers to detect a reduction of 50% or more in the levels of MHBMA, 3-HPMA, S-PMA, and COHb on Day 5 and in total NNAL after 90 days in smokers switching from CC to the CHTP 1.2 as compared to smokers continuing to use CC, using a one-sided test with 2.5% type I error probability using the assumptions from YVD-CS01-EU, and 120 randomized subjects in a 2:1 ratio (80 in CHTP 1.2 arm and 40 in CC arm) are described in [Table 23](#).

Table 23 Test-Wise Power

Parameter	Test-Wise Power
COHb	96%
3-HPMA	>99%
MHBMA	>99%
S-PMA	>99%
Total NNAL	98%

Given the above calculation, the sample size was considered sufficient to have more than 80% power to detect a reduction of 50% or more in the levels of MHBMA, 3-HPMA, S-PMA, and COHb in CHTP 1.2 arm compared to the CC arm after 5 days of exposure, and in the levels of total NNAL in the CHTP 1.2 arm compared to the CC arm after 90 days of exposure, using a one sided test with 2.5% type I error probability.

